NCT02526186

Document date: 5/29/2018

Battlefield Auricular Acupuncture for Control of Post-partum Pain

PROTOCOL FOR CLINICAL INVESTIGATION – NON-EXEMPT HUMAN PROTOCOL SUMMARY

1. Title:

Battlefield Auricular acupuncture for control of post-partum pain.
FWH20150072H

2.0. Principal Investigator (PI):

PI:	
Name	[name]
Rank/Corps or Civilian Rating	Col
Date of IRB Approved CITI Training & Date of Good Clinical Practice Training	12/28/17
Branch of Service	USAF
AD Mil/DoD Civilian/Ctr/Non-DoD Civ	AD Mil
Department & Base	Family Medicine Residency, Nellis AFB
Phone & [contact]
E-Mail Address & AKO/DKO E-Mail Address	[contact]

3.0. Research Plan:

3.1. Purpose:

The purpose of this study is to compare battlefield auricular acupuncture plus standard of care versus standard of care in the reduction of pain, use of pharmacological analgesics, and satisfaction with experience in mothers in the immediate post-partum period.

3.2. Hypotheses, Research Questions or Objectives:

Does battlefield auricular acupuncture provide significant pain control for mothers in the immediate post-partum period?

4. Brief Summary of the study:

We will conduct a randomized controlled trial to determine whether the addition of battlefield auricular acupuncture to standard of care is effective for control of postpartum pain for mothers in the immediate post-partum period. Post-partum patients (DoD beneficiaries) 18 years or older, regardless of gravida/parity, who plan to have a childbirth in a hospital setting will be offered the opportunity to participate in the study through PCM referrals and posted advertisements. After a minimum of 6 hours post-vaginal delivery or 24 hours post caesarean section subjects will be given treatment according to their randomization group. Subjects will be assessed on pain control, overall satisfaction with pain management, and the amount of pharmacological pain medications used. Safety of measures will also be assessed to include infection rates, syncope, vertigo, and hypotension.

5. Subjects:

Post-partum females (DoD beneficiaries). Age 18 years or older, will be recruited at the Mike O'Callaghan Military Medical Center. No other special populations (e.g., children, military basic trainees, prisoners, detainees) will be recruited.

6. Inclusion/exclusion criteria:

Inclusion:

- Post-partum female (DoD beneficiaries).
- Age 18 years or older
- Pain score rating post-delivery of greater or equal to 4/10.

Exclusion:

- Absence of one or more ears
- Active cellulitis of ear
- Ear anatomy precluding identification of acupuncture landmarks
- Non-English speaking
- Use of Hearing Aids that preclude the use of ear acupuncture
- Known allergy to gold

7. Number of Subjects: TOTAL NUMBER OF SUBJECTS (nation-wide/study-wide): Nellis 90

8. Use of an Investigational New Drug: N/A

9. Use of an Investigational Device: Sedatelec ASP Original Gold Acupuncture needles, 510(k) exempt as Class II device under 21 CFR 880.5580

10. Use of a Placebo: N/A

PROTOCOL FOR CLINICAL INVESTIGATION – NON-EXEMPT HUMAN

1. Title:

Battlefield Auricular acupuncture for control of post partum pain.

FWH20150072H

2.0. Principal Investigator (PI):

PI:	
Name	[name]
Rank/Corps or Civilian Rating	Col
Date of IRB Approved CITI Training & Date of Good Clinical Practice Training	12/28/17
Branch of Service	USAF
AD Mil/DoD Civilian/Ctr/Non-DoD Civ	AD Mil
Department & Base	Family Medicine Residency, Nellis AFB
Phone & [contact]
E-Mail Address & AKO/DKO E-Mail Address	[contact]

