2.1. Associate Investigators (AI): See form A2 Study Personnel

2.2. Research Assistants (RA) & Coordinators (RC): See form A2 Study Personnel

2.3. The research relevance of this protocol focuses on:

Diagnosis Treatment Medical Utilization/Managed Care Prevention Medical Readiness Other

2.4. Location(s):

- Collaborating Facilities: N/A
- Air Force Sites seeking Regional IRB: [name], [contact]
- List study sponsors: N/A

3. Research Plan:

3.1. Purpose:

The purpose of this study is to compare battlefield auricular acupuncture plus standard of care versus standard of care in the reduction of pain, use of pharmacological analgesics, and satisfaction with experience in mothers in the immediate post-partum period.

3.2. Hypotheses, Research Questions or Objectives:

Does battlefield auricular acupuncture provide significant pain control for mothers in the immediate post-partum period?

3.3. Significance:

If effective, battlefield auricular acupuncture techniques can be used as a safe method of pain control in the immediate post-partum period and result in greater satisfaction with the labor and delivery experience as well as reduce complications associated with increased pharmacological interventions.

3.4. Military Relevance:

This research will directly benefit the healthcare of active duty members and beneficiaries who undergo delivery in the DoD healthcare system. Given the cost savings in avoiding pharmacological medications or other invasive interventions, this study may also provide long-term health care cost savings and improve mission efficiency.

3.5. Background and Review of Literature:

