- **Group 2:** Standard of care plus Battlefield acupuncture at treatment sites Cingulate gyrus, thalamus, omega 2, shen-men, point zero in both ears (see figures 1-5). The 5 needles will remain in each ear for up to 7 days or allowed to fall out on their own (the patient will be instructed not to remove the needles).
 - Subject's ears will be cleansed with an alcohol swab
 - Subjects will be given a handout of standard BFA Discharge Instructions including what an infection looks like and what to do in the event of an infection (see attached).

Visit 1: Will occur after a minimum of 6 hours post vaginal birth (up until hospital discharge) to avoid disturbing maternal infant bonding or a minimum of 24 hours post caesarean section to avoid confounding with the anesthesia:

- Subject will be given treatment according to their randomization group.
- All subjects, regardless of randomization group, will be instructed to have no heavy meals, no excessive hot or cold foods, no heavy exercise or intercourse, and no alcohol for 6 hours.
- Satisfaction with post-partum pain management will be assessed with the following questions:
 - On a scale of 0 to 10, how satisfied were you with your pain management after delivery? (dissatisfied 0 – 10 very satisfied)
 - Would you use auricular acupuncture for future pain management? (Yes or no) (for those in the acupuncture group only)
 - On a scale of 0-10, with 10 being the worst pain, what is your level of pain?

In hospital data collection:

Data will be collected each day until the patient has been discharged from the hospital. Subjects will be contacted either in person or via phone and the hospital stay will vary from patient to patient:

- We will review the subject's medical record and record RN Recorded Pain assessments, Delivery method (either Caesarean section or spontaneous vaginal delivery), Delivery complications (vaginal lacerations, use of episiotomy, operative vaginal delivery, shoulder dystocia, post-partum hemorrhage), Birth weight, Maternal Parity, and record what pain medications they are taking.
- We will ask subjects if they prefer to be contacted in-person or via telephone while in the hospital.
- Satisfaction with post-partum pain management will be assessed with the following questions:
 - On a scale of 0 to 10, how satisfied were you with your pain management after delivery? (dissatisfied 0 – 10 very satisfied)

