 - Would you use auricular acupuncture for future pain management? (Yes or no) (for those in the acupuncture group only)
 - On a scale of 0-10, with 10 being the worst pain, what is your level of pain?
 - Are the needles still in place? If yes, how many in each ear?

Post hospital discharge:

Each day up until 10 days post Visit 1. Subjects will be contacted phone and the following information will be collected:

[figure not shown]
- Satisfaction with post-partum pain management will be assessed with the following questions:
 - On a scale of 0 to 10, how satisfied were you with your pain management after delivery? (dissatisfied 0 – 10 very satisfied)
 - Would you use auricular acupuncture for future pain management? (Yes or no) (for those in the acupuncture group only)
 - On a scale of 0-10, with 10 being the worst pain, what is your level of pain?
- We will record what pain medications they are taking including drug name, strength, and total doses since discharge from the hospital.

Placement of Battlefield Acupuncture:

Battlefield auricular acupuncture utilizes up to 10 needles (see figure 6). The ear Acupuncture points include Cingulate gyrus, thalamus, omega 2, shen-men, point zero (see figures 1-5). The subject will receive five needles on each ear. Intermittent placement checks by the medical acupuncturist will be performed.

The acupuncture being performed in this study is a standard acupuncture technique for the treatment of pain. The physicians performing the treatment are trained in this acupuncture technique. As such, all physicians trained in this procedure will be able to perform the acupuncture for treatment of research subjects.

The Food and Drug Administration (FDA) regulates acupuncture needles as a class II medical device, because they are intended for use in the cure, mitigation, treatment, or prevention of disease in man or are intended to affect the structure or function of the body of man. The FDA regulates the acupuncture needles (see 21 CFR 880.5580), but not the practice of acupuncture itself. The needles being used are Sedatelec ASP Original Gold needles, which are exempt from premarket notification by the FDA for use in acupuncture and will be used in accordance with their FDA approved labeling.

3.6.1. Interventions, Observations, or Data Sought:

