4.7. Costs: N/A

4.8. Safeguards for Protecting Information:

The research consents will be stored in a locked cabinet in a locked room. Medical records will be annotated with ICD-10 code Z00.6 to reflect the subject's participation in a research study. All research data including patient demographics will be kept in an electronic database, which will be encrypted, double password protected and the access will be restricted. The research

data will be de-identified and any links to identifiable data will be destroyed as soon as possible. The research data will not be utilized for further research activity beyond the protocol stipulations without additional IRB approval.

4.9. Safeguards for Protecting Subjects:

The principal investigator will be responsible for the protocol safety monitoring. The PI will make study documents (e.g., consent forms, data pulls) and pertinent hospital or clinical records readily available for inspection by the local IRB and oversight staff for confirmation of the study data.

4.9.1. Minimizing Risks:

These risks will be minimized by cleaning the acupuncture site with an alcohol swab prior to placement. If at any time the patient reports a side effect, they will be referred to one of the Investigators for care.

4.9.2. Vulnerable Populations:

This research will not involve any treatment decisions related to the pregnancy or viability of the nonate, and if such questions come up, the Principle Investigator (PI) will refer the subject to their Primary Care Manager (PCM) and will not participate in any pregnancy or neonate-related decision making or guidance.

4.9.3. Clinical Care:

All subjects will receive standard of care regardless of inclusion into this study. If at any time a subject experiences any injury or adverse effects, appropriate clinical care will be given or subject will be referred to appropriate provider.

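### Four safety measures are promised, but no readable data-collection list asks for or extracts them and no safety outcome or analysis is planned, so non-serious events are likely under-counted by an unknown amount

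*Combined protocol and SAP*

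**What the plan says.** The protocol summary, section 4, makes the commitment: "Safety of measures will also be assessed to include infection rates, syncope, vertigo, and hypotension". A rate of infection implies that infection is looked for in a defined group over a defined period.

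The collection steps are in section 3.6:

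- **Visit 1.** The list opens "Satisfaction with post-partum pain management will be assessed with the following questions" and covers satisfaction, willingness to use acupuncture again (Group 2 only) and pain.
- **In hospital, record review.** "We will review the subject's medical record and record RN Recorded Pain assessments, Delivery method (either Caesarean section or spontaneous vaginal delivery), Delivery complications", followed by birth weight, parity and pain medications.
- **In hospital, questions.** The same three as Visit 1, plus "Are the needles still in place? If yes, how many in each ear".
- **After discharge.** "Subjects will be contacted phone and the following information will be collected". The readable items are the same three questions and pain medications. A figure at the head of this list is not shown.

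On side effects, section 4.9.1 says: "If at any time the patient reports a side effect, they will be referred to one of the Investigators for care". The Group 2 description in section 3.6 adds: "Subjects will be given a handout of standard BFA Discharge Instructions including what an infection looks like". No such handout is listed for Group 1. Section 3.3 says that, if effective, "battlefield auricular acupuncture techniques can be used as a safe method of pain control in the immediate post-partum period".

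**The concern.** A stated assessment has no matching data item. If staff follow the readable lists exactly, a count of zero for fainting, vertigo, hypotension or ear infection could mean that none occurred or that nobody asked. The report could not tell these apart.

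Ear infection and hypotension show the gap most clearly. Needles may stay in for up to 7 days, and follow-up runs to 10 days after Visit 1, so much of the exposure can fall after discharge, when the telephone call is the only scheduled contact. Hypotension needs a blood pressure reading, but vital signs appear only in the screening record review.

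Efficacy is not affected. What is at stake is whether the trial can report the safety rates it promises, and whether a low count would carry any weight.

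**Working it through.** **Step 1. Set the promise against each list.**

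| Place | What is collected | Any of the four events? |
|---|---|---|
| 3.6, screening | History, including vital signs, before treatment | No post-treatment reading |
| 3.6, Visit 1 | Satisfaction, future use, pain | None |
| 3.6, in-hospital record review | Nurse-recorded pain, delivery data, birth weight, parity, pain medications | None |
| 3.6, in-hospital questions | Satisfaction, future use, pain, needle retention | None |
| 3.6, post-discharge calls | Satisfaction, future use, pain, pain medications | None readable; one figure not shown |
| 3.6.1 | Standard-of-care items, satisfaction, pain, pain medicines | None |
| 6.1 and 6.3 | Outcomes on pain, medication and satisfaction; ROC and repeated-measures analysis | None |

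The needle question records retention, not the state of the ear. Section 4.6 names infection as a risk but not syncope, vertigo or hypotension. The attachment list in section 13 names no adverse-event form.

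**Step 2. Other routes by which an event could be recorded.** Section 3.6 provides occasional needle-placement checks, with no schedule and no safety finding to record. Section 4.9.5 has monitoring meetings that verify reporting of serious adverse events and compare study records with nurses' notes and hospital charts. These could pick up some events, mainly in hospital. None is set up to count the four.

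**Step 3. Inputs for the illustration.** The plan gives no safety rate, safety sample size or safety precision, so there is no safety figure to reproduce. Section 6.4 gives 90 enrolled and 66 completing (24/90 = 26.7% loss). No allocation ratio is stated. I assume an equal split: 90/2 = 45 enrolled and 66/2 = 33 completing in the acupuncture arm. The share of events captured, s, is not in the documents, so a range is shown.

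**Step 4. Upper bound when no event is recorded.** If the true rate is p and each event is captured with probability s, the chance of recording none in n women is (1 − p·s)^n. Setting this to 0.05 gives p = [1 − 0.05^(1/n)] / s.

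| Capture s (assumed) | n = 45 | n = 33 |
|---|---|---|
| 100% | 6.4% | 8.7% |
| 75% | 6.44/0.75 = 8.6% | 8.68/0.75 = 11.6% |
| 50% | 6.44/0.50 = 12.9% | 8.68/0.50 = 17.4% |
| 25% | 6.44/0.25 = 25.8% | 8.68/0.25 = 34.7% |

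**Step 5. Chance of recording at least one event**, 1 − (1 − p·s)^45, for assumed true rates:

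| True rate p (assumed) | s = 100% | 75% | 50% | 25% |
|---|---|---|---|---|
| 2% | 60% | 49% | 36% | 20% |
| 5% | 90% | 82% | 68% | 43% |
| 10% | 99% | 97% | 90% | 68% |

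At a true rate of 5%, 45 × 0.05 = 2.25 events are expected. With full capture the arm would very probably show at least one. With a quarter captured, it would more likely than not show none.

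**The case against.** Several points on the other side have force.

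- **The post-discharge list has a figure that cannot be seen.** It sits directly after the words introducing what will be collected, at the stage where ear infection matters most. A safety item there cannot be ruled out. Section 3.6.1 names only pain and medicines for the follow-up contact, which points the other way, but it is a summary and also leaves out satisfaction after discharge. The caveat stands for the calls. It does not touch Visit 1, the in-hospital lists, 6.1 or 6.3.
- **A reader might infer that patient report is the only way an event can be counted.** The documents do not say so. Section 4.9.1 is a rule about referral for care, not about counting, and the routes in step 2 exist.
- **A reader might infer that the safety rates will certainly be too low.** Neither an event rate nor a capture share is given, so only likely under-counting of unknown size is supported.
- **A reader might take section 3.3 as a planned safety conclusion.** It is a conditional statement of significance, and the purpose in 3.1 does not include safety.
- **A handout for women who have needles is natural.** That is fair. If it raises infection reporting in Group 2, it works against under-counting of that event there. Bias in the between-arm comparison could therefore run either way.
- **The sample is small in any case.** Zero events in 45 leaves a bound of 6.4% even with full capture, and better collection cannot reduce that. It can stop the bound from widening by an unknown factor.

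**Conclusion.** The point holds in a limited form. The protocol summary commits to assessing four safety measures, and no readable contact list, record review, outcome or analysis provides for them. Followed as written, the readable plan cannot deliver those rates. Non-serious events are likely under-counted, chiefly after discharge, and infection may be ascertained differently in the two arms.

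The size is unknown. For zero recorded infections among an assumed 45 acupuncture women, the one-sided 95% upper bound runs from 6.4% with full capture to 25.8% with a quarter captured. These figures rest on equal allocation, an assumed range of capture, no false reports and independent capture of each event. They illustrate the effect and do not estimate it.

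The change should be made because it is cheap and supplies what the plan already promises. The efficacy comparison does not depend on it.

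**What to change.** 1. Add separate yes/no items, each with a date and a short definition, for fainting, vertigo and signs of ear infection to every contact already scheduled, with identical wording in both arms. Keep them separate: one combined question could not give a rate for each event. Define infection signs so that they are distinct from insertion-site pain, which section 4.6 lists as likely.
2. Add blood pressures recorded after Visit 1 to the in-hospital record review already planned, with a definition of hypotension, for counting purposes, fixed before data are examined.
3. List the four events in section 6.1 as safety outcomes, and state in 6.3 that they will be reported as counts by arm with exact confidence intervals.
4. If the figure missing from the post-discharge list already contains a safety item, align its wording with the other contacts.

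The cost is a slightly longer contact, extra fields in an existing chart review and a short amendment. More minor events will be recorded, and the report should say that they were solicited. Clinical care does not change.

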2.1. Associate Investigators (AI): See form A2 Study Personnel

2.2. Research Assistants (RA) & Coordinators (RC): See form A2 Study Personnel

2.3. The research relevance of this protocol focuses on:

Diagnosis Treatment Medical Utilization/Managed Care Prevention Medical Readiness Other

2.4. Location(s):

- Collaborating Facilities: N/A
- Air Force Sites seeking Regional IRB: [name], [contact]
- List study sponsors: N/A

3. Research Plan:

3.1. Purpose:

The purpose of this study is to compare battlefield auricular acupuncture plus standard of care versus standard of care in the reduction of pain, use of pharmacological analgesics, and satisfaction with experience in mothers in the immediate post-partum period.

3.2. Hypotheses, Research Questions or Objectives:

Does battlefield auricular acupuncture provide significant pain control for mothers in the immediate post-partum period?

3.3. Significance:

If effective, battlefield auricular acupuncture techniques can be used as a safe method of pain control in the immediate post-partum period and result in greater satisfaction with the labor and delivery experience as well as reduce complications associated with increased pharmacological interventions.

3.4. Military Relevance:

This research will directly benefit the healthcare of active duty members and beneficiaries who undergo delivery in the DoD healthcare system. Given the cost savings in avoiding pharmacological medications or other invasive interventions, this study may also provide long-term health care cost savings and improve mission efficiency.

3.5. Background and Review of Literature:

Acupuncture is one of the oldest medical procedures still practiced regularly today. There is a diverse array of styles and techniques that speak to the specific culture and era in which it was developed. While the exact proposed mechanism of action of acupuncture on pain is not completely elucidated, it is clear that there are profound physiological effects. Specifically, stimulation with acupuncture excites nerve fibers that cause the release of endogenous opioids and oxytocin that result in functional changes in multiple organ systems. Beta-endorphin levels have been known to regulate pain control, blood pressure, and body temperatures have been observed to increase in the brain tissues after acupuncture (1). Functional MRI studies have also demonstrated increased activation in specific regions of the brain that correlates with established acupuncture and electro acupuncture points compared against sham points (2, 3). Auricular acupuncture follows this same premise and refers to piquering various points on the ear that are believed to have functional effects to targeted areas of the body to achieve the desired result.

Ear acupuncture (referred to as Battlefield Acupuncture or “BFA” in this study) is a technique developed by Niemtzow (4) and refers to piquering 5 specific points on the ear with semi-permanent acupuncture needles for acute pain relief. As opposed to traditional auricular acupuncture, this technique uses a simple, systematic approach to placing the needles that can be learned by providers in a short amount of time. Because the needles are semi-permanent, the needles stay in place after the patient leaves the encounter and are allowed to fall out on their own over time. BFA is widely used today and has been taught at the Helms Medical Institute acupuncture course, Uniformed Services Academy of Family Physicians Annual Conference, and at the Malcom Grow Medical Center Acupuncture Clinic. While the use of ear acupuncture specifically has limited data to support its effectiveness, there is a growing body of evidence to support the use of auricular acupuncture as an effective modality in relieving acute pain. This includes pain in the intra and post-operative period (5, 6, 7), low back pain and pelvic pain associated with pregnancy (8), and migraines (9).

